# **Background and Introduction**

Venous thromboembolism, which encompasses both deep vein thrombosis (DVT) and pulmonary embolism (PE), is a potentially devastating post-operative complication. VTE results in approximately 100,000 deaths per year, a number higher than the annual mortality from breast cancer and motor vehicle accidents combined. PE results in 5-10% of hospital deaths, making it one of the most common preventable causes of in-hospital death. The rates of VTE after orthopaedic surgery are as high as 40-60% without prophylactic measures. Polytrauma, older age, obesity, prolonged operative time, and prolonged bed-rest are some factors that put surgical patients at higher risk. Enoxaparin chemoprophylaxis has been shown to result in a four-fold reduction in DVT rates in post-operative orthopaedic trauma.

The American College of Chest Physicians (ACCP) and American Academy of Orthopedic Surgeons (AAOS) have issued guidelines for thromboprophylaxis following total knee arthroplasty, total hip arthroplasty, and hip fracture surgery (HFS). These guides lack specific recommendations for other high-risk injuries including pelvic, acetabular, or femur fractures. The Orthopaedic Trauma Association (OTA) has published an expert panel consensus on prophylaxis in the orthopaedic trauma population, however. Even with these guides though, the optimal strategy to prevent post-operative VTE remains unclear. Drug choice, drug dosing, duration of prophylaxis, and the degree of anti-coagulation are all still debated. The 2012 ACCP guidelines in HFS, for example, recommend the use of one of several agents including low molecular weight heparins, unfractionated heparin, warfarin, or aspirin for 10 to 35 days, leaving the surgeon left to decide the exact drug and duration. The OTA and AAOS favor enoxaparin as drug of choice, but are equally non-specific on duration and make no recommendations for specific orthopaedic injuries.

Enoxaparin, a low-molecular-weight heparin (LMWH), produces an anticoagulant effect by binding antithrombin, thereby accelerating antithrombin's inactivation of coagulation factor Xa (FXa), thus decreasing the likelihood of clot formation. Current recommended prophylactic dosing of enoxaparin is either 30mg twice daily (BID) or 40mg daily (QD). While not currently part of the standard of care, steady state peak and trough anti-Factor Xa (aFXa) levels can be used to monitor enoxaparin activity. On twice daily dosing, a steady state peak range of 0.2-0.4 IU/mL and trough of > 0.1 IU/mL have been shown to maximize VTE risk reduction in non-orthopaedic populations.

Despite standard dosing enoxaparin prophylaxis, VTE rates in post-operative orthopaedic trauma patients remain as high as 12.2%. It is not known why some patients suffer from breakthrough VTE events despite standard prophylaxis. Current prophylaxis guidelines do not adequately address these individuals. The use of standardized enoxaparin dosing is has been challenged by a data from a prior study by this group as well as several other surgical fields. Body weight and the extent of thermal or surgical injury have been shown to correlate with anti-Xa levels in thermally injured, critically ill, and obese patients

#### Unpublished data from prior study on standard enoxaparin dosing in orthopaedic trauma

From May 2016 to May 2017, 109 unique post-operative orthopaedic trauma patients were enrolled and obtained appropriately timed peak aFXa levels. Fifty eight (53%) had initial peak aFXa levels within the goal range of 0.2-0.4 IU/mL while 15 (19%) had initial aFXa trough within goal range >0.1 IU/mL. Real-time dose adjustment was successful in achieving goal peak aFXa in and additional 14 of 20, resulting in 72 of 109 (66.1%) achieving goal steady-state peak aFXa levels. Ninety-eight patients (89.9%) were discharge from the hospital on some duration of outpatient enoxaparin, 25 (25.5%) of which were receiving doses that were inadequate based on aFXa level (aFXa <0.2 IU/mL).

Eighty-eight patients have reached the 90-day mark post-operatively as of May 15, 2017. Eleven patients were lost to follow-up (no clinic visits and unreachable by phone) leaving 90-day follow up data available for 77 patients (87.5%). There were no re-operative bleed events and there were two minor bleed events while on anticoagulation, including one patient with a heavy menses and one with a positive guiac but no identified GI bleed.

Seven VTE events occurred, including 4 DVTs and 3 PEs in 5 patients (n 109, rate 4.6%). One DVT occurred in a patient who was within the goal peak aFXa range on initial blood draws (n 58, 1.7%). The remaining 6 VTE events occurred in 4 patients who had initial peak aFXa levels below goal range (n 47, 8.5%). Our data demonstrated that 43% of patients received inadequate prophylaxis in response to 30mg BID enoxaparin dosing and that a moderate correlation ( $R^2 = 0.46$ ) exists between weight and peak aFXa in response to a fixed dose. Four patients were considered to be over anticoagulated (>0.4 IU/mL).

This study would examine if a weight based enoxaparin protocol could elevate the number of post-operative orthopaedic trauma patients receiving adequate chemoprophylaxsis. It aims to see if the orthopaedic trauma service can increase the number of patients that start on adequate prophylaxis and increase the number of patients that get discharged on appropriate doses. Two VTE events occurred while patients in the prior study were undergoing enoxaparin dose adjustment. These may have been avoided if the patients received an initial enoxaparin doses that were weight based rather than of standard dosing. Ultimately this study may aid in our understanding why breakthrough VTE events occur and hopefully become part of a means to reduce breakthrough occurrences.

## **Purpose and Objectives**

The American College of Chest Physicians and American Academy of Orthopaedic Surgeons recommend post-operative venous thromboembolism (VTE) prophylaxis in certain orthopaedic trauma patients to lower the risk of DVT and PE. 30mg twice daily (BID) or 40mg once daily (QD) of enoxaparin is commonly used as chemoprophylaxis and has shown efficacy in reducing VTE rates in post-operative patients. Based on steady state anti-Factor Xa (aFXa), a marker of enoxaparin activity, obese, critically ill, and thermally injured patients are often provided inadequate prophylaxis on these standard enoxaparin doses. In joint replacement and trauma populations, inadequate steady-state aFXa levels have been associated with an increase in DVT rates. Despite enoxaparin prophylaxis, VTE rates remain as high as 12.2% in orthopaedic trauma. These events can represent a significant financial burden to hospitals and can be life or limb threatening for patients. Existing data from our group and others suggest that inadequate enoxaparin dosing, quantified by xFXa levels, represents a plausible explanatory mechanism for some of these "breakthrough" VTE events.

A previous study by this group examined the association between standard enoxaparin dosing (30mg BID) and steady state aFXa levels in orthopaedic trauma and found an association with inadequate aFXa levels and VTE events. A correlation was found between patient weight and their peak aFXa level. No association was found between aFXa and major bleed events. Based on these data, a weight-based protocol was adopted on for enoxaparin prophylaxis on the orthopaedic trauma service. The current study aims to examine how a weight-based dosing protocol alters the steady state aFXa in orthopaedic trauma patients as well as their risk for VTE and major bleed events.

Aim 1: Evaluate peak steady-state aFXa levels in response to weight-based enoxaparin prophylaxis (0.4mg/kg twice daily) in orthopaedic trauma patients.

Rationale: More than 12% of orthopaedic trauma patients experience breakthrough VTE events despite standard dose enoxaparin prophylaxis. Fixed dose enoxaparin prophylaxis has been shown to be inadequate in orthopaedic trauma surgery and several other surgical subspecialties. Prior data from this group showed that 53% of orthopaedic trauma patients were within goal peak aFXa range.

Hypothesis: Initial peak steady-state aFXa levels will be within the accepted range (0.2-0.4 IU/mL) in 75% of patients on weight-based enoxaparin dosing in orthopaedic trauma patients, up from 53% on fixed 30mg BID dosing.

Aim 2: Examine the response of aFXa levels to a real-time dose adjustment protocol.

Rationale: Literature in several surgical subspecialties shows that dose adjustment can significantly increase the number of patients within goal the peak aFXa range. Data from this group showed that dose adjustment achieved an increase in the number of patient within range

from 53% to 66%.

Hypothesis 2: Protocol-driven enoxaparin dose adjustment in response to aFXa levels will increase the proportion of patients with appropriate aFXa peak levels to from 75% to 85%.

Aim 3: Examine rates of 90-day VTE and clinically relevant bleeding events in orthopaedic trauma patients on weight-based enoxaparin prophylaxis.

Rationale: This observational aim will allow us to better understand VTE and bleeding rates after orthopaedic trauma surgery. Events have been shown to be rare and we recognize that the proposed study is underpowered to rigorously examine alterations in VTE or bleed rates in response to the proposed dose adjustment protocol.

Hypothesis 3: Rates of post-operative VTE and re-operative bleeds will be < 2% in each group.

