# Statistical Methods, Data Analysis and Interpretation

The proportion of patients with in-range peak aFXa levels using fixed vs. weight-based dosing will be compared with the chi-squared test. The impact of real time enoxaparin dose adjustment will be examined by comparing the proportion of patients with in-range aFXa levels before and after dose adjustment. Time series analysis will examine associations between initial in-range and out-of-range aFXa levels and downstream VTE and/or major bleeding events.

Our projected recruitment results in inadequate power to examine VTE prevention or major bleeding events in response to enoxaparin dose escalation (one of our aims). This study will provide important preliminary data for weight-based dosing in orthopaedic trauma, which to our knowledge has not been done in orthopaedic surgery to date. We will collect data on 90-day symptomatic VTE events, 90-day major bleeding events (re-operative hematoma), and time to VTE or major bleeding event. We will contact patients at 90 days via telephone or certified mail to identify events that were diagnosed or managed at other institutions.

Sample size calculation:

Retention from our previous study in orthopaedic trauma was 72%. 151 patients were enrolled, 22 discharged prior to lab draws, 8 were changed from enoxaparin to an alternative blood thinner prior to lab draws, and 12 underwent blood draws but had unusable data as the draws were inappropriately timed (<3hrs or >5hrs after 3rd enoxaparin dose for steady-state peak xFXa level). Of these remaining 109 patients, 53% had initial peak aFXa levels within our goal range of 0.2-0.4IU/mL. Dose adjustment achieved adequate prophylaxis in an additional 13% of patients. Our hypothesis is that 75% of patients will be within range with weight-based dosing. Using an alpha of 0.05 and beta of 0.9, we would need 107 patients to effectively power a similar change for peak aFXa levels in the proposed study. With 28% over enrollment to allow for attrition, we would require n = 137.

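### Aim 3's pooled in-range versus out-of-range comparison cannot inform on bleeding, and the prior cohort's bleeding null came from zero major bleeds

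*Combined protocol and SAP*

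**What the plan says.** Purpose and Objectives summarises the earlier fixed-dose cohort in three findings. The study "found an association with inadequate aFXa levels and VTE events"; weight correlated with peak aFXa; and, on safety, "No association was found between aFXa and major bleed events". The text continues: "Based on these data, a weight-based protocol was adopted on for enoxaparin prophylaxis on the orthopaedic trauma service".

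The section on unpublished prior data gives the counts. On bleeding: "There were no re-operative bleed events and there were two minor bleed events while on anticoagulation", with 90-day follow-up on 77 patients. Four patients were above 0.4 IU/mL. VTE occurred in 1 of 58 patients in range and 4 of 47 below range. No test, p-value or interval accompanies either statement.

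For the new study, Statistical Methods plans that "Time series analysis will examine associations between initial in-range and out-of-range aFXa levels and downstream VTE and/or major bleeding events". It collects "90-day major bleeding events (re-operative hematoma"), so a major bleed means a re-operative one. Hypothesis 3 expects VTE and re-operative bleeds each below 2% per group, without defining the groups or attaching an interval. The Aim 3 rationale and Statistical Methods both say the study is underpowered for VTE and bleeding.

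**The concern.** With no major bleeds the outcome does not vary, and no method can estimate or test its relation to aFXa. Reporting this as a finding of no association presents missing information as a negative result. The VTE sentence has a milder form of the problem: the difference is large, but it rests on five patients.

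This matters for the new study because Statistical Methods plans the same kind of analysis in a cohort of similar size. It also puts below-range and above-range patients into one out-of-range group. Bleeding risk would be expected to move in opposite directions at the two ends, so pooling dilutes the signal that a safety analysis should look for. The plan does not say how zero or few events will be reported. At stake is what Aim 3 can legitimately conclude about bleeding, and whether an uninformative null is carried forward as reassurance a second time.

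**Working it through.** **1. The plan's own figures.** From the prior-data section: 58 in range + 47 below + 4 above = 109. VTE patients: 5/109 = 4.6%, 1/58 = 1.7%, 4/47 = 8.5%. All reproduce. Since 1 + 4 = 5, no VTE patient was above range.

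**2. Prior cohort, bleeding.** With zero events in n, the exact two-sided 95% upper limit is 1 − 0.025^(1/n).
- n = 77 (followed to 90 days): 4.7%
- n = 109 (all with valid peaks): 3.3%
- n = 4 (above range, if all four were followed, which the document does not say): 60%

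**3. Prior cohort, VTE.** Risk ratio = (4/47)/(1/58) = 4.94. SE of its log = √(1/4 − 1/47 + 1/1 − 1/58) = 1.10. The 95% CI is exp(1.597 ± 1.96 × 1.10), about 0.57 to 43.

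| Comparison (patients) | Test | p |
|---|---|---|
| Below v in range, 4/47 v 1/58 | Fisher | 0.17 |
| same | Pearson chi-squared | 0.10 |
| same | Yates | 0.24 |
| Below v all others, 4/47 v 1/62 | Fisher | 0.16 |
| Out of v in range, 4/51 v 1/58 | Fisher | 0.18 |

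Counting events instead of patients (6 v 1) gives Fisher p = 0.043, but this treats repeat events in one patient as independent.

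The VTE rates use all 109 patients, although only 77 had 90-day data. If all five VTE patients were among the 77, Fisher p falls below 0.05 only if 27 or fewer of the 77 were below range. A proportional split is 77 × 47/109 ≈ 33, with p = 0.16.

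**4. New study, planned contrast for bleeding.** Evaluable n = 107 and 75% hypothesised in range, so 107 × 0.75 ≈ 80 in range and 27 out. Assume 5 of the 27 are above range (the prior share, 4/109, would give about 4), with bleeding risk 10% above range and 1% elsewhere.
- Average risk out of range: (22 × 0.01 + 5 × 0.10)/27 = 0.72/27 = 2.7%. Pooling turns a ten-fold risk into a 2.7-fold one.
- Expected bleeds: 0.72 out of range and 80 × 0.01 = 0.80 in range.
- With no bleeds in range, 2 out-of-range bleeds give Fisher p = (27 × 26)/(107 × 106) = 0.062. It takes 3, about four times the expected number, to reach p < 0.05: (27 × 26 × 25)/(107 × 106 × 105) = 0.015.
- Exact two-sided Fisher power at 0.05: about 3% for 80 v 27, and about 20% for above range v the rest (5 v 102).

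**5. Hypothesis 3.** Exact upper limits with zero events:
- 0/107: 3.4% two-sided, 2.8% one-sided
- 0/94 (107 × 0.875, assuming the earlier follow-up rate): 3.8% two-sided
- if the groups are in and out of range at 80 and 27 (assumed): 4.5% and 12.8% two-sided

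None excludes 2%. With zero events, excluding 2% needs 149 patients (one-sided 95%) or 183 (two-sided).

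**The case against.** The strongest reply has four parts.

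- **The rationale does not rest on these two sentences.** The weight–aFXa correlation (R² = 0.46), the 53% in-range rate and outside literature all support trying weight-based dosing. This stands. A reader might infer that the case for the protocol falls once the two sentences are corrected; the documents do not support that.
- **Association need not mean statistical significance.** A risk ratio of 4.9 is an association descriptively, the counts are disclosed, and the unpublished study may have modelled aFXa as a continuous variable. This also stands for VTE. A reader might infer that levels and VTE are unrelated; an interval of 0.57 to 43 does not show that. The reply cannot rescue the bleeding sentence, because no model estimates a relation from zero events.
- **Low power is already admitted.** Aim 3 is called observational and underpowered, and the study is described as giving preliminary data. So a reader should not infer an undisclosed flaw, or that the plan commits itself to claiming safety. But the admission in Statistical Methods is framed around dose escalation, and the one in Aim 3 around the dose-adjustment protocol. Neither says how a null level-event result will be reported, and neither addresses the pooling.
- **The power figures use assumed inputs.** True: the five above-range patients, the two risks and the 80/27 split are all assumptions. They illustrate the planned contrast and do not forecast it. The direction is firmer than the size, since pooling a small high-level group with a larger low-level one can only dilute an excess bleeding risk confined to high levels.

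**Conclusion.** The concern holds as a minor one. The earlier cohort could not assess aFXa against major bleeding: there were no such bleeds (upper 95% limit 4.7% on 77 followed, 3.3% on 109) and only 4 patients above range. Its VTE difference is suggestive and not established by the reported counts, subject to the unknown analysis method.

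In the new study, the pooled contrast would have about 3% power against a ten-fold bleeding risk at high levels, and an above-range contrast about 20%, under the assumptions stated. A null from either would say almost nothing. Even 0/107 leaves an upper limit of 3.4%, so an observed rate below 2% would not show that the true rate is below 2%.

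The sample size, the Aim 1 comparison and the laboratory endpoint do not depend on any of this.

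**What to change.** In Statistical Methods, replace the pooled contrast for Aim 3 with patient-level event counts and exact 95% limits shown separately below, in and above range, for VTE and for major bleeding. Define the groups in Hypothesis 3 and report their rates with exact limits. Add one sentence saying that zero or few events will be reported as a relation that could not be assessed, and not as absence of association. No minimum event count is needed, because the exact limits show how little is known.

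As a consequential edit, align the two sentences in Purpose and Objectives with the counts. For bleeding: no re-operative bleeds and four patients above range, so the relation could not be assessed. For VTE: 4/47 v 1/58, risk ratio 4.9, 95% CI 0.6 to 43, suggestive only; if the earlier study used another analysis, name it and give its result.

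The cost is a few sentences and limits computed from data already being collected; no extra patients or procedures are needed. The downside is that the rationale and Aim 3 read as less settled.

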## **Study Population**

#### Age of Participants: 18+

#### Sample Size:

At Utah: 137 All Centers:

#### **Inclusion Criteria:**

We will include adult patients who have undergone orthopaedic trauma surgery and can have enoxaparin initiated within 36 hours after procedure. All patients will undergo informed consent.

#### **Exclusion Criteria:**

We will exclude those with intracranial bleeding/stroke, bleeding disorder, heparin-induced thrombocytopenia, creatinine clearance  $\leq 30$ mL/min, epidural catheter, or serum creatinine >1.6mg/dL.

### Design

Prospective Clinical Research

### **Study Procedures**

#### **Recruitment/Participant Identification Process:**

Daily operative schedule will be reviewed for University of Utah orthopaedic trauma surgeons to identify post operative trauma patients. Once identified, patients will be approached by [name] or the study clinical research coordinators ([name], [name]) to undergo the informed consent process.

## Informed Consent: Description of location(s) where consent will be obtained:

University of Utah Hospital

#### Description of the consent process(es), including the timing of consent:

Patients will be identified based on the daily surgery schedule and followed to see if they are started on enoxaparin post operatively at the discretion of the surgeon. Patients will undergo the informed consent process on post-operative day one or two while admitted to the hospital. No waiting period between the consent process and obtaining consent is planned, unless requested by the patient.

#### Procedures performed for research purposes only:

The surgery is standard of care. The decision to have surgery or not is part of the standard care and has nothing to do with the research process.

Provision of post-operative enoxaparin is standard of care. The decision (yes/no) to give enoxaparin by the surgeon is not part of this study.

The non standard of care procedures for this study include:

- 1. Blood draws for anti-Factor Xa levels after surgery (generally 2-4 blood draws per patie
- 2. Possible Enoxaparin dose adjustment based on anti-Factor Xa level

# Statistical Methods, Data Analysis and Interpretation

The proportion of patients with in-range peak aFXa levels using fixed vs. weight-based dosing will be compared with the chi-squared test. The impact of real time enoxaparin dose adjustment will be examined by comparing the proportion of patients with in-range aFXa levels before and after dose adjustment. Time series analysis will examine associations between initial in-range and out-of-range aFXa levels and downstream VTE and/or major bleeding events.

Our projected recruitment results in inadequate power to examine VTE prevention or major bleeding events in response to enoxaparin dose escalation (one of our aims). This study will provide important preliminary data for weight-based dosing in orthopaedic trauma, which to our knowledge has not been done in orthopaedic surgery to date. We will collect data on 90-day symptomatic VTE events, 90-day major bleeding events (re-operative hematoma), and time to VTE or major bleeding event. We will contact patients at 90 days via telephone or certified mail to identify events that were diagnosed or managed at other institutions.

Sample size calculation:

Retention from our previous study in orthopaedic trauma was 72%. 151 patients were enrolled, 22 discharged prior to lab draws, 8 were changed from enoxaparin to an alternative blood thinner prior to lab draws, and 12 underwent blood draws but had unusable data as the draws were inappropriately timed (<3hrs or >5hrs after 3rd enoxaparin dose for steady-state peak xFXa level). Of these remaining 109 patients, 53% had initial peak aFXa levels within our goal range of 0.2-0.4IU/mL. Dose adjustment achieved adequate prophylaxis in an additional 13% of patients. Our hypothesis is that 75% of patients will be within range with weight-based dosing. Using an alpha of 0.05 and beta of 0.9, we would need 107 patients to effectively power a similar change for peak aFXa levels in the proposed study. With 28% over enrollment to allow for attrition, we would require n = 137.

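### The target of 137 multiplies 107 by 1.28 instead of dividing by 0.72, so it projects to about 99 evaluable patients, and beta of 0.9 should read power 0.90 (minor)

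*Combined protocol and SAP*

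**What the plan says.** All the relevant text is in the combined protocol and SAP.

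- **Retention.** The sample size calculation, under Statistical Methods, Data Analysis and Interpretation, takes 72% retention from the previous study and counts it from enrolment: "151 patients were enrolled, 22 discharged prior to lab draws", then 8 switched to another anticoagulant and 12 with mistimed draws, leaving 109.
- **Evaluable number.** For in-range proportions of 53% and 75%, it says: "Using an alpha of 0.05 and beta of 0.9, we would need 107 patients to effectively power a similar change".
- **Enrolment target.** "With 28% over enrollment to allow for attrition, we would require n = 137". The Sample Size entry under Study Population repeats the figure: "At Utah: 137 All Centers".
- **Test.** "The proportion of patients with in-range peak aFXa levels using fixed vs. weight-based dosing will be compared with the chi-squared test". The plan does not mention sidedness or continuity correction.
- **Comparator.** The section on unpublished prior data reports, for the 109 fixed-dose patients: "Fifty eight (53%) had initial peak aFXa levels within the goal range of 0.2-0.4 IU/mL".

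**The concern.** Two things are wrong as written.

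First, the loss rate and the inflation use different denominators. The 28% is a fraction of patients enrolled, but the plan applies it as a percentage of patients evaluable. A 28% loss from 137 does not leave 107, so the plan's 107, 72% and 137 cannot all hold together.

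Second, beta is the type II error rate. A beta of 0.9 means 10% power, which is plainly not intended and does not lead to 107.

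This paragraph is the plan's only sample size justification. A reader cannot tell from it whether 99 evaluable patients would be the expected outcome or a shortfall, nor what power the enrolment target delivers.

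**Working it through.** **Inputs.** From the sample size calculation: 151 enrolled; losses 22, 8 and 12; 53% against 75%; alpha 0.05; 107 needed; 137 to enrol. From the prior-data section: 58 of 109 in range. Assumed here: a two-sided test.

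**1. Reproduce 107.** With p1 = 0.53, p2 = 0.75, mean 0.64 and equal groups, the uncorrected number per group at power 0.90 is

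n = [1.960 × √(2 × 0.64 × 0.36) + 1.2816 × √(0.53 × 0.47 + 0.75 × 0.25)]² / 0.22² = (1.3305 + 0.8468)² / 0.0484 = 97.9, or 98.

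With continuity correction:

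(97.9/4) × [1 + √(1 + 4/(97.9 × 0.22))]² = 106.8, or 107.

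The same formulas in other settings give:

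| Setting | Uncorrected | Corrected |
|---|---|---|
| Two-sided, power 0.90 | 98 | **107** |
| Two-sided, power 0.80 | 74 | 83 |
| One-sided, power 0.90 | 80 | 89 |
| One-sided, power 0.80 | 58 | 67 |
| Two-sided, beta literally 0.9 (power 0.10) | 5 | 13 |

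Only the two-sided, corrected, 90% power version gives 107. With the comparator fixed at 109, 90% power needs 90 new patients uncorrected or 105 corrected, so 107 is an equal-groups answer.

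**2. Reproduce 137.** 107 × 1.28 = 136.96, or 137.

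**3. Apply the plan's own retention.**

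- 151 − 22 − 8 − 12 = 109, and 109/151 = 72.2%.
- Enrolment that would yield 107: 107/0.72 = 148.6, or 149.
- Evaluable from 137: 137 × 0.72 = 98.6, or about 99. This is 8 fewer than 107 (8/107 = 7.5%).
- Retention at which 137 yields 107: 107/137 = 78.1%.
- If the evaluable count is binomial with size 137 and probability 109/151, the chance of 107 or more is 7.1%, and the 95% range is 88 to 109.

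**4. Effect on power.** The actual comparator is the 109 prior patients. With 99 new patients the pooled proportion is (109 × 0.53 + 99 × 0.75)/208 = 0.6347, the null standard error is 0.06685 and the alternative standard error is 0.06465.

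- Uncorrected: z = (0.22 − 1.960 × 0.06685)/0.06465 = 1.376, power 91.6%.
- Corrected: 0.22 is reduced by ½(1/109 + 1/99) = 0.00964, so z = 1.227, power 89.0%.

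The range over retention:

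| Retention of 137 | Evaluable | Uncorrected | Corrected |
|---|---|---|---|
| 65% | 89 | 89.9% | 87.0% |
| 72% | 99 | 91.6% | 89.0% |
| 75% | 103 | 92.1% | 89.7% |
| 78.1% | 107 | 92.6% | 90.3% |
| 80% | 110 | 92.9% | 90.8% |

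Exact enumeration at 99 agrees (91.7% and 89.1%). These are ordinary two-sample planning values. Conditional on the 58/109 already observed and a true 75%, power at 99 is higher: 97.6% uncorrected, 96.1% corrected.

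**The case against.** The best defence is that almost nothing turns on this. The plan names a chi-squared test without a correction, and by that test 99 evaluable patients against 109 still exceed 90% power. No reader would take beta of 0.9 literally beside a sample size of 107. Both statements are right, and they are why the point is minor. They do not make the text correct: the 28% allowance is stated to cover attrition, and at the only attrition rate the plan gives it does not.

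Three further points deserve weight.

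- **The method behind 107 is inferred.** The plan does not state two-sidedness, continuity correction or equal groups, nor that 107 is per group. The match also uses the rounded 53%; with 58/109 the same formula gives 109. This stands, so the sponsor must confirm those details.
- **Like for like, the loss is somewhat larger.** In the equal-groups, corrected framework that yields 107, power at 99 per group is 87.4%. The 109 prior patients are the real comparator, so 89.0% is the more relevant corrected figure, but it too is just under 90%.
- **Retention may improve.** Of the 42 losses, 12 were mistimed draws. The documents promise no improvement, however, and the plan itself budgets for 28%.

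**Conclusion.** The concern holds, as a minor error. The enrolment target comes from multiplying by 1.28 where the plan's own retention calls for dividing by 0.72, so 137 projects to about 99 evaluable patients, not 107. The error rate is mislabelled: the figure meant is power 0.90, beta 0.10.

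The cost at 72% retention is about 1 percentage point of power against the 109 prior patients: 92.6% to 91.6% uncorrected, or 90.3% to 89.0% corrected. Under the chi-squared test as worded, 137 still meets 90% power.

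This rests on recurrence of the 72% retention, a two-sided 5% level, and 53% against 75%. The inflation arithmetic depends only on the plan's stated numbers.

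**What to change.** Keep 137 and restate the paragraph so that its figures agree, for example:

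> Using an alpha of 0.05 (two-sided; sponsor to confirm) and power of 0.90 (beta 0.10), a comparison of 53% with 75%, with equal groups and continuity correction (both for the sponsor to confirm), requires 107 evaluable patients per group. We will enrol 137 (107 × 1.28), which yields 107 evaluable if at least 78.1% are retained. If the previous study's 72% retention recurs, about 99 will be evaluable. Against the 109 prior fixed-dose patients, 99 gives planning power of about 92% (uncorrected chi-squared test) or about 89% (continuity-corrected).

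The analysis text should also say whether the chi-squared test will be continuity-corrected. If the sponsor prefers to hold 107 as the expected evaluable number, the consistent target is 149, which is 12 more patients; the uncorrected test does not need them to reach 90% power.

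The recommended change is wording only, with no additional enrolment.
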